##### Endpoints analyzed:

- Change from baseline in European Organisation for Research and Treatment of Cancer Quality of Life Questionnaire Core 30 items (EORTC QLQ-C30):

This analysis will be performed for the Intention-to-Treat population (ITT). For the following endpoints, change from baseline is defined as the post-treatment value minus the value at baseline. The % change from baseline will be calculated as:

$$(\text{Postbaseline value} - \text{baseline value}) / \text{baseline value} \times 100.$$

The **EORTC QLQ-C30 v3 questionnaire** is included for the purpose of assessing HRQoL and is a well-established measure of HRQoL/health status. It assesses HRQoL/health status through 9 multi-item scales: 5 functional scales (physical, role, cognitive, emotional, and social), 3 symptom scales (fatigue, pain, and nausea and vomiting), and a global health and quality-of-life (QoL) scale. Six single-item symptom measures are also included dyspnea, insomnia, appetite loss, constipation, diarrhea, and financial difficulties. For each of the 15 domains, final scores are transformed such that they range from 0 to 100, where higher scores indicate greater functioning, greater HRQoL, or greater level of symptoms .

The principle for scoring these scales is the same in all cases:

- Estimate the average of the items that contribute to the scale; this is the raw score.
- Use a linear transformation to standardise the raw score, so that scores range from 0 to 100; a higher score represents a higher ("better") level of functioning, or a higher ("worse") level of symptoms.

For all scales, the *RawScore*, *RS*, is the mean of the component items:

$$\text{RawScore} = \text{RS} = (I_1 + I_2 + \dots + I_n)/n$$

Then for **Functional scales**:

$$\text{Score} = \left\{ 1 - \frac{(\text{RS} - 1)}{\text{range}} \right\} \times 100$$

For **Symptom scales/ items** and **Global health status/ QoL**:

$$\text{Score} = \left\{ \frac{(\text{RS} - 1)}{\text{range}} \right\} \times 100$$

The following outcomes will be analysed for this endpoint:

- Time to symptom deterioration: defined as the time from start of study drug until the date of the first clinically meaningful symptom deterioration (a decrease in the score from baseline of  $\geq 10$  points) that is confirmed at the subsequent assessment (at least 14 days apart) or death (by any cause) in the absence of a clinically meaningful symptom deterioration, regardless of whether the patient withdraws from study drug or receives another anticancer therapy prior to symptom deterioration. Death will be included as an event only if the death occurs within 2 visits of the last PRO assessment where the symptom change could be evaluated.  
Patients whose QoL (as measured by EORTC QLQ-C30) have not shown a clinically meaningful deterioration and who are alive at the time of the analysis will be censored at the time of their last PRO assessment where the QoL/function could be evaluated. Also, if QoL deteriorates after 2 or more missed PRO assessment visits or the patient dies after 2 or more missed PRO assessment visits, the patient will be censored at the time of the last PRO assessment where QoL/function could be evaluated. If a patient has no evaluable visits or does not have baseline data, he/she will be censored at Day 1.
- Time to quality of life/ function deterioration: defined as the time from start of study drug until the date of the first clinically meaningful deterioration (a decrease in the function scales or the global health status/QoL from baseline of  $\geq 10$  points) that is confirmed at the subsequent assessment (at least 14 days apart) or death (by any cause) in the absence of a clinically meaningful deterioration, regardless of whether the patient withdraws from study drug or receives another anticancer therapy prior to QoL/function deterioration. Death will be included as an event only if the death occurs within 2 visits of the last PRO assessment where the QoL/function change could be evaluated.
- Symptom improvement rate: defined as the number (%) of patients with 2 consecutive assessments at least 14 days apart that show a clinically meaningful improvement (an increase from baseline score  $\geq 10$  points for EORTC QLQ-C30 symptom scales/items) in that symptom from baseline.
- Quality of life/function improvement rate: defined as the number (%) of patients with 2 consecutive assessments at least 14 days apart that show a clinically meaningful improvement (an increase from baseline score  $\geq 10$  points for EORTC QLQ-C30 functional scales and global health status/QoL) in that scale from baseline.
- Change from baseline in European Organisation for Research and Treatment of Cancer Quality of Life. Questionnaire-Lung Cancer 13 (EORTC QLQLC13):

This analysis will be performed for the Intention-to-Treat population (ITT). For patients with SCLC, a disease-specific 13-item self-administered questionnaire for lung cancer was developed to be used in conjunction with the EORTC QLQ-C30. It comprises both multi-item and single-item measures of lung cancer-associated symptoms (i.e., coughing, haemoptysis, dyspnoea, and pain) and side effects from conventional

chemotherapy and radiotherapy (i.e., hair loss, neuropathy, sore mouth, and dysphagia). Similar to the EORTC QLQ-C30, all questions except one have a 4-point scale: (not at all, a little, quite a bit and very much). One question (no. 43, —Did you take any medicine for pain?) has a response option (Yes; No). The scoring approach for the EORTC QLQ-LC13 is similar to the EORTC QLQ-C30.

The following outcomes will be analysed for this endpoint:

- Time to symptom deterioration
- Symptom improvement rate

- Changes from baseline in PRO-CTCAE:

The **PRO-CTCAE** is included to address tolerability from the patients' perspective. It was developed in recognition that collecting symptom data directly from patients using PRO tools can improve the accuracy and efficiency of symptomatic AE data collection.

In this study, only items that are considered relevant for the study, site of cancer, and cancer treatment are selected.

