PFS (days) = Date of event or Censor date – treatment start date +1

Patients who have not progressed or died at the time of analysis will be censored at the time of the latest date of assessment from their last evaluable assessment. However, if the patient progresses or dies after 2 or more missed visits, the patient will be censored at the time of the latest evaluable assessment prior to the 2 missed visits. If the patient has no evaluable visits or does not have baseline data, he/she will be censored at Day 1 unless he/she dies within 2 visits of baseline, in which case the date of death is the event date.

OS: Defined as the time from the first date of treatment until death due to any cause.

OS (days) = Death date or Censor date - treatment start date +1

Any patient not known to have died at the time of analysis will be censored based on the last recorded date on which the patient was known to be alive.

ORR: Based on Investigator–assessed response to treatment of CR and PR, per RECIST1.1.

DoR: Defined as the time from the date of first documented response per RECIST1.1 until the first date of documented progression per RECIST1.1 or death in the absence of disease progression.

DoR (days) = Date of PFS event or censoring – Date of first response +1

The end of response should coincide with the date of progression or death from any cause used for the PFS endpoint. If a patient does not progress following a response, then the patients' DoR will be censored at the PFS censoring time. DoR will not be defined for those patients who do not have a documented response.

Time to symptom deterioration (EORTC QLC-C30 and QLC-LC13): Defined as the time from start of study drug until the date of the first clinically meaningful symptom deterioration that is confirmed at the subsequent assessment or death (by any cause) in the absence of a clinically meaningful symptom deterioration, regardless of whether the patient withdraws from study drug or receives another anticancer therapy prior to symptom deterioration.

Change from baseline (EORTC QLC-C30 and QLC-LC13, PRO-CTCAE): Defined as the post-treatment value minus the value at baseline. The % change from baseline will be calculated as (postbaseline value - baseline value) / baseline value x 100.

Treatment duration: Defined as Treatment end date - Treatment start date +1; will be summarized.

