## **5. ANALYSIS METHODS**

Descriptive statistics will be used for all variables, as appropriate. Continuous variables will be summarized by the number of observations, mean, standard deviation, median, quartiles (Q1 and Q3), minimum, and maximum. Categorical variables will be summarized by frequency counts and percentages for each category. The number of missing data will be provided for every analysed variable.

Missing values will not be considered for calculating percentages or any other descriptive, meaning that only valid values will be presented. No use of any method for the handling of missing data is foreseen.

For patients excluded from the statistical analyses, descriptive of the reasons for non-evaluability will be provided.

The software package SAS version 9.4 will be used for data analysis.

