#### Endpoints analyzed:

- Change from baseline in European Organisation for Research and Treatment of Cancer Quality of Life Questionnaire Core 30 items (EORTC QLQ-C30) and Questionnaire-Lung Cancer 13 (EORTC QLQLC13):

Scores for the QLQ-C30 and QLQ-LC13 questionnaires will be calculated according to published scoring manuals or the developer's guidelines. Raw scores from scales in both questionnaires will be standardized by linear transformation so that they range from 0 to 100. Higher scores for symptom items indicate greater symptom severity, while higher scores for function and global health status/QoL items indicate better function and health status/QoL. For both questionnaires, a clinically meaningful change will be prespecified as an absolute change in score from baseline of  $\geq 10$  points (either deterioration or improvement). For the five key disease-related symptoms (cough, dyspnea, and chest pain [QLQ-LC13], and fatigue and appetite loss [QLQ-C30]), changes at each visit from baseline to disease progression or end of follow-up (whichever came first) will be analyzed using a mixed model for repeated measures (MMRM) to derive an overall adjusted mean change from baseline, reflecting the average treatment effect over visits. The model assumes PROs will be collected at multiple visits per

patient. Visits with >75% missing data will be excluded from the analysis. The MMRM included treatment, age at baseline (<65 vs ≥65 years), sex, smoking history (smoker vs non-smoker) and visit interaction as fixed factors, and baseline score as a covariate; the model further adjusted for baseline score-by-visit interaction.

Summaries of original and change from baseline values of each symptom scale/item, the global HRQoL score, and each functional domain will be reported by visit.

Time to symptom deterioration and time to quality of life / function deterioration (defined in 4.2.2) will be analyzed by product limit methods to provide summaries of the number and percentage of patients experiencing a clinically meaningful deterioration or death, the median time to deterioration together with the corresponding 95% CIs, as well as the Kaplan-Meier plot. An stratified log-rank test adjusted for therapy will be used with HR s and 95% CIs calculated using a stratified Cox proportional hazards model.

Symptom improvement rate and Quality of life / function improvement (defined in 4.2.2) will be summarized.

- Changes from baseline in PRO-CTCAE:

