PRO-CTCAE data will be presented using summaries and descriptive statistics for categorical data for each question of the questionnaire.

### 5.2.3 Secondary outcome 3

- To describe health care resources use related to management of ES-SCLC patients treated with durvalumab in combination with platinum- etoposide as first-line treatment. It will be described the overall costs and health care resources use as well as costs and health care resources use adjusted by time in years.

The following data will be described as appropriate:

- Number of hospitalizations (Categorical and continuous)
- Length of hospitalizations: time from date of admission to discharge date (Continuous).
- Number of visits to oncology service (Categorical and continuous)
- Number of emergency visits (Categorical and continuous)
- Number of outpatients visits (Categorical and continuous)
- Number of imaging tests (Categorical and continuous)
- Number of biopsy-related procedures (Categorical and continuous)
- Listing of treatments administered, including: Treatment name, dose, duration and number of cycles
- Assessment of health economic resource: Costs associated with HCRU use will be quantified by multiplying the natural units of use of each resource by the cost of each resource retrieved from Spanish databases

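### Percent change from baseline is prescribed for 0-100 EORTC scores that can be 0 at baseline, so the statistic is undefined for some patients and asymmetric for the rest

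*SAP*

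**What the plan says.** SAP 4.2.2.2, under the QLQ-C30 endpoint, first defines change as the post-treatment score minus the baseline score, then adds: "The % change from baseline will be calculated as" that difference over the baseline value, times 100. Protocol 9.4 has the same rule, "The % change from baseline will be calculated as (postbaseline value - baseline value) / baseline value x 100", under an entry that names QLQ-C30, QLQ-LC13 and PRO-CTCAE.

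The scores in the denominator are bounded: "final scores are transformed such that they range from 0 to 100" (SAP 4.2.2.2). On direction, "Higher scores for symptom items indicate greater symptom severity" (SAP 5.2.2), while higher functional and global scores are better.

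On values that cannot be used, SAP section 5 states "Missing values will not be considered for calculating percentages or any other descriptive", and SAP 6.2 repeats this and foresees no imputation. Neither document mentions a baseline of 0.

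For PRO-CTCAE, SAP 5.2.2 takes a different route from protocol 9.4: "PRO-CTCAE data will be presented using summaries and descriptive statistics for categorical data for each question of the questionnaire".

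**The concern.** A percent change needs a denominator that is positive and has a meaningful zero. EORTC scores meet neither need. They are linear rescalings of ordinal answers, and one end of the scale is set to 0.

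Two things follow if the formula is run as written. First, patients with a baseline of 0 have no percent change. On a symptom scale these are the patients who can only stay the same or get worse, so leaving them out tilts the summary towards improvement. On the functional and global scales they are the most impaired patients, who can only stay the same or improve, so the tilt goes the other way. The same column would exclude opposite kinds of patient on different scales. Second, among the patients who remain, a given number of points counts for more when the baseline is low.

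At stake is a descriptive patient-reported table that could disagree with the absolute-change table beside it, even in sign.

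**Working it through.** **Inputs.** Scoring formulas: SAP 4.2.2.2. Item codes 1 to 4, with 1 for no symptom: protocol Appendices H and I. Single items: "Six single-item symptom measures are also included dyspnea, insomnia, appetite loss, constipation, diarrhea, and financial difficulties" (SAP 4.2.2.2), plus most QLQ-LC13 items. Percent-change formula: SAP 4.2.2.2 and protocol 9.4. The SAP does not define range; I read it as highest minus lowest code, which is 3 for these items.

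**Step 1: reproduce the 0-100 range.** With RS the mean of the items:
- Symptom score = (RS - 1)/3 x 100. RS = 1, 2, 3, 4 gives 0, 33.3, 66.7, 100.
- Functional score = {1 - (RS - 1)/3} x 100. RS = 1, 2, 3, 4 gives 100, 66.7, 33.3, 0.
- Global health uses the symptom formula, so RS = 1 gives 0 whatever the range. With items assumed to be coded 1 to 7 (range 6), it runs from 0 to 100.

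The stated range is reproduced, and 0 is an attainable baseline on every scale.

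**Step 2: percent change for a single symptom item.**

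| Baseline | Post 0 | Post 33.3 | Post 66.7 | Post 100 |
|---|---|---|---|---|
| 0 | undefined | undefined | undefined | undefined |
| 33.3 | -100% | 0% | +100% | +200% |
| 66.7 | -100% | -50% | 0% | +50% |
| 100 | -100% | -66.7% | -33.3% | 0% |

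In points every cell is defined; the first row is 0, +33.3, +66.7, +100.

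**Step 3: asymmetry.** One patient goes from 33.3 to 66.7: (66.7 - 33.3)/33.3 = +100%. Another goes from 66.7 to 33.3: (33.3 - 66.7)/66.7 = -50%. Mean percent change is (100 - 50)/2 = +25%; mean absolute change is 0 points.

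A fall is capped at -100%, but a rise is not. With k four-level items the lowest non-zero score is s = 100/(3k), and the largest rise is (100 - s)/s:
- k = 1: s = 33.3, up to +200%
- k = 2: s = 16.7, up to +500%
- k = 3: s = 11.1, up to +800%

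**Step 4: effect of leaving out zero baselines (illustration only).** The documents do not give the share at 0. Assume 85 patients, the planned number, and one single-item symptom. Half of the zero-baseline patients worsen by one level; everyone else starts at 33.3 and half of them fall to 0. Each group then moves by half of 33.3, that is 16.7 points, in opposite directions. With n0 patients at 0, the mean absolute change over all patients is 16.7 x {n0 - (85 - n0)}/85.

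| Share at 0 | Left out (n0) | Mean % change, those kept | Mean absolute change, all |
|---|---|---|---|
| 10% | 8 | -50% | -13.5 |
| 30% | 26 | -50% | -6.5 |
| 50% | 42 | -50% | -0.2 |
| 70% | 59 | -50% | +6.5 |
| 90% | 76 | -50% | +13.1 |

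The percent figure does not move while the true average change turns from improvement to worsening. Steps 3 and 4 can pull in opposite directions, so the net direction of the distortion in real data is not fixed.

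**The case against.** The strongest reply is that nothing planned depends on this formula. After giving it, SAP 4.2.2.2 lists times to deterioration and improvement rates, all based on changes of at least 10 points. SAP 5.2.2 specifies by-visit summaries of original and change values and a mixed model on change from baseline. No table, model or figure in SAP section 5 names percent change. This stands, and it sets the limit of the point.

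A reader might infer that new-onset toxicity such as sore mouth, neuropathy or hair loss is lost, and that the safety question suffers. The documents do not support that. Protocol 9.5.2.3(b) requires by-visit original and change values for these side effects, so a patient going from 0 to 100 counts there as +100 points. The primary safety endpoints, grade 3 or higher and immune-mediated events, come from the adverse-event section of the eCRF (SAP 4.2.1 and 5.1).

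It is also fair to say that the exclusion is inferred. The missing-data text does not say that an undefined ratio of two observed scores counts as missing. But no other written rule covers such patients, and a ratio with no value cannot enter a mean or a median. SAP section 5 also asks for medians and quartiles, which are less sensitive to large ratios than the mean in step 3; they do not restore the patients left out.

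On PRO-CTCAE, the SAP already prescribes categorical summaries and protocol 9.5.2.3(c) defers to the SAP. Only the mention in protocol 9.4 is out of line. A shift table would be a matter of presentation, not a correction.

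**Conclusion.** The formula is wrong as written, with narrow reach. Both documents say that it will be calculated, it has no value at an attainable baseline, and it fits poorly with the plan's own measure of meaningful change, which is an absolute change of at least 10 points. If it is run, the output can mislead; if it is not run, that is an unexplained departure from the plan.

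The certain part follows from the SAP's scoring: undefined at 0, and +100% against -50% for the same step up and down. The removal of zero-baseline patients rests on reading the valid-values rule as applying to undefined ratios. How many patients this would affect is unknown; the 8 to 76 of 85 in the illustration reflects assumed shares of 10% to 90% and assumed transitions, and is not an estimate for this study.

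The absolute-change summaries, the mixed model, times to deterioration, improvement rates and primary adverse-event endpoints are unaffected. It would go too far to read this as a flaw in the safety analysis or in the patient-reported results as a whole.

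**What to change.** Delete the percent-change sentence and formula from SAP 4.2.2.2 and from protocol 9.4, and rely on the absolute change in points that SAP 5.2.2 and protocol 9.5.2.3 already plan. Removing the formula from protocol 9.4 also takes PRO-CTCAE out of it, so the protocol then agrees with the categorical summaries in SAP 5.2.2.

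If the sponsor wants to keep a percent change for some scale, the SAP should state how a baseline of 0 is handled and report, by scale and visit, how many patients are excluded for that reason.

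The cost is a text deletion in each document. No planned analysis changes and no information is lost. If the protocol text has to wait for the next amendment, a line in the SAP saying that percent change will not be produced would cover the interval.

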For each of the symptoms scales/items in the EORTC QLQ-C30 questionnaire, time to symptom deterioration will be defined as the time from start of study drug until the date of the first clinically meaningful symptom deterioration (an increase in the score from baseline of ≥ 10 points) that is confirmed at the subsequent assessment (at least 14 days apart) or death (by any cause) in the absence of a clinically meaningful symptom deterioration, regardless of whether the patient withdraws from study drug or receives another anticancer therapy prior to symptom deterioration. Death will be included as an event only if the death occurs within 2 visits of the last PRO assessment where the symptom change could be evaluated.

Patients with a single deterioration and no further assessments will be treated as deteriorated in the analysis. Patients whose symptoms (as measured by EORTC QLQ-C30) have not shown a clinically meaningful deterioration and who are alive at the time of the analysis will be censored at the time of their last PRO assessment where the symptom could be evaluated. Also, if symptoms deteriorate after 2 or more missed PRO assessment visits or the patient dies after 2 or more missed PRO

assessment visits, the patient will be censored at the time of the last PRO assessment where the symptom could be evaluated. If a patient has no evaluable visits or does not have baseline data, he/she will be censored at Day 1.

The analysis of time to symptom deterioration will be done with a subset of patients who have baseline scores of ≤ 90 .

Time to quality of life/function deterioration

For QoL, time to deterioration will be defined as the time from start of study drug until the date of the first clinically meaningful deterioration (a decrease in the function scales or the global health status/QoL from baseline of ≥ 10 points) that is confirmed at the subsequent assessment (at least 14 days apart) or death (by any cause) in the absence of a clinically meaningful deterioration, regardless of whether the patient withdraws from study drug or receives another anticancer therapy prior to QoL/function deterioration. Death will be included as an event only if the death occurs within 2 visits of the last PRO assessment where the QoL/function change could be evaluated.

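### SAP 4.2.2.2 reverses symptom deterioration and symptom improvement: a falling symptom score, which means relief, is counted as deterioration

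*SAP*

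**What the plan says.** **Scale direction.** The scoring rule in SAP 4.2.2.2 makes a high symptom score the bad end of the 0–100 scale and defines change as post-treatment minus baseline. SAP 5.2.2 repeats the direction: "Higher scores for symptom items indicate greater symptom severity".

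**SAP definitions.** SAP 4.2.2.2 defines time to symptom deterioration by "the first clinically meaningful symptom deterioration (a decrease in the score from baseline of" at least 10 points. Its symptom improvement rate counts patients whose assessments "show a clinically meaningful improvement (an increase from baseline score" by at least 10 points, and it names the QLQ-C30 symptom scales/items explicitly.

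**Protocol definitions.** The text of protocol 9.5.2.3 has the opposite signs. Its event is the "first clinically meaningful symptom deterioration (an increase in the score from baseline of" at least 10 points, and its symptom improvement rate requires a fall. In the same section, the table captioned Table 14 labels a symptom change of +10 or more as improvement and −10 or less as deterioration.

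**Analysis section.** SAP 5.2.2 gives the 10-point threshold as an absolute change, without a sign, and sends the analysis back to section 4: "Time to symptom deterioration and time to quality of life / function deterioration (defined in 4.2.2".

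**The concern.** The definitions are the reverse of what they name. A patient whose cough becomes steadily worse would count toward the improvement rate, and a patient whose cough resolves would be a deterioration event.

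The result would not even be a mirror image that could be relabelled afterwards. A death within two visits of the last evaluable questionnaire is an event whichever sign is used, so the curve would be a composite of symptom relief and death, with no clinical meaning.

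The report would also contradict itself. For cough, dyspnea, chest pain, fatigue and appetite loss, changes "will be analyzed using a mixed model for repeated measures" on the signed score, which stays correct, as do the by-visit summaries. The same symptom could worsen in one table and improve in another.

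The impact on symptoms is a stated secondary objective, and protocol 9.5.2.3 pre-specifies time to deterioration for seven key symptoms: cough, hemoptysis, dyspnea and chest pain from QLQ-LC13, and insomnia, fatigue and appetite loss from QLQ-C30.

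**Working it through.** The plan gives no figure to reproduce. The check sets the definitions against the SAP's own scoring formula.

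**1. Sign of a worsening.** SAP 4.2.2.2: symptom score = ((RS − 1)/range) × 100, where RS is the mean of the items. Items are answered 1 to 4 (protocol Appendices H and I), so range = 3. A patient going from *Not at all* (1) to *Very much* (4) moves from (0/3) × 100 = 0 to (3/3) × 100 = 100, a change of +100. Worsening is therefore positive.

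**2. Definitions side by side.**

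| Source | Symptom deterioration | Symptom improvement | Fits the scoring rule? |
|---|---|---|---|
| SAP 4.2.2.2 | fall ≥10 | rise ≥10 | No |
| Protocol 9.5.2.3, text | rise ≥10 | fall ≥10 | Yes |
| Protocol 9.5.2.3, table captioned Table 14, symptom row | ≤ −10 | ≥ +10 | No |
| SAP 5.2.2 | absolute change ≥10 | absolute change ≥10 | Gives no sign; refers back to 4.2.2 |

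**3. Which direction was meant.** Protocol 9.5.2.3 restricts time to symptom deterioration to patients with a baseline score of 90 or less. On a 0–100 scale, a rise of 10 is impossible only from a baseline above 90, so the restriction fits a rule based on a rise. A rule based on a fall would instead need a baseline of at least 10. Under the SAP rule, a patient without the symptom at baseline (score 0) can never have a score-based deterioration event, however severe the symptom becomes.

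**4. Which changes are misclassified.**

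- Single item: 4 levels (0, 33.3, 66.7, 100). 4 × 4 = 16 baseline/post pairs, less 4 unchanged, leaves 12 (6 worse, 6 better). The smallest change is 33.3.
- Two-item scale: 7 levels, step 100/6 = 16.7. 49 − 7 = 42 changes.
- Three-item scale (for example LC13 dyspnea, items 33–35): 10 levels, step 100/9 = 11.1. 100 − 10 = 90 changes (45 worse, 45 better).

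Every step exceeds 10 points, so all 12, 42 and 90 changes cross the threshold. Each is put in the opposite class by the SAP and by the protocol text, once it is confirmed or sustained over two assessments at least 14 days apart.

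**5. Outputs affected.**

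- QLQ-C30, using the list in protocol 9.5.2.3: 3 scales + 5 items = 8; 8 × 2 endpoints = 16.
- QLQ-LC13, by inference: 6 symptoms + 4 side effects = 10; 10 × 2 = 20.
- Total: 16 + 20 = 36.

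SAP 4.2.2.2 gives QLQ-LC13 the same two endpoints without defining them, and says only that "The scoring approach for the EORTC QLQ-LC13 is similar to the EORTC QLQ-C30".

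**The case against.** The reversal itself cannot be argued away: the words are plain prose, and neither redaction nor a broken table explains them. The fair objections concern scope and weight.

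- **QLQ-LC13 is inferred.** The SAP's improvement definition names QLQ-C30 only, and protocol 9.5.2.3 ties QLQ-LC13 to the protocol's own correct rule. A programmer could apply the right sign there. This stands: 16 outputs and three of the seven key symptoms are directly affected, and the rest depends on the inference.
- **The count is not exact.** The SAP lists six single-item measures, including financial difficulties, where the protocol's analysis list has five. Counting it would add two outputs. This does not alter the conclusion.
- **The counts of score changes are not an effect size.** True. They show that no threshold-crossing change escapes the error; they do not show how far a median or rate would move.
- **A hazard ratio has little meaning here anyway.** There is one treatment arm and no comparator, so distortion of the HR adds little. The point rests on the Kaplan-Meier summaries and improvement rates.
- **An attentive programmer would notice,** because SAP 5.2.2 states the scale direction. Possibly, but the protocol defers the detail of this analysis to the SAP, and quietly departing from a written definition would itself be a deviation.
- **The table carries little weight.** The SAP lists no output based on the protocol's visit-response categories, so that correction is less urgent.

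**Conclusion.** Wrong as written. Both symptom definitions in SAP 4.2.2.2 contradict the SAP's own scoring rule and the protocol text, and nothing else in the SAP corrects them. Programmed literally, all confirmed threshold-crossing symptom changes are misclassified in 16 QLQ-C30 outputs, and in 36 outputs if QLQ-LC13 follows the same rule. The size of the distortion in any median or rate cannot be given without event rates, and none are assumed.

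The error is confined to secondary, descriptive outcomes. Grade ≥3 AEs, imAEs, function and global QoL endpoints, PRO-CTCAE, the mixed model and the by-visit summaries are not touched. The definitions still need correcting before any symptom output is produced or relied on.

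**What to change.** In SAP 4.2.2.2, define symptom deterioration as a rise of at least 10 points and symptom improvement as a fall of at least 10 points. Add one sentence saying that both apply to the symptom scales and items of QLQ-C30 and QLQ-LC13.

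SAP section 7 schedules a QoL output covering section 5.2.2 for February 2022. If it was run under these definitions, rerun its time-to-symptom-deterioration and symptom-improvement results.

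At the next protocol amendment, exchange the two labels in the symptom row of the visit-response table in 9.5.2.3. Cite it by its caption, because the text calls it Table 15 and the list of tables gives number 14 to another table.

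While the section is open, some smaller alignments are worth making:

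- carry the protocol's baseline ≤90 subset into the SAP;
- carry over its rule that a single deterioration with no later assessment is an event;
- make the SAP's censoring text under symptom deterioration refer to symptoms rather than QoL/function;
- correct the statement in protocol 9.5.2.3 that an effective treatment shortens time to deterioration; it should lengthen it.

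The cost is two phrases and one sentence in the SAP, plus any rerun. The protocol correction needs ethics committee approval (Appendix A 1) and can wait for an amendment made for other reasons. No new data are needed and patients are not affected.
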